### **Suspected Unexpected Serious Adverse Reaction (SUSAR)**

A serious adverse event that is suspected to be related to the administered medicinal product and the nature or severity of which is not consistent with the reference safety information.

### **Adverse Events of Special Interest**

NT-814 is a non-hormonal therapy and so is not expected to have any adverse effect on the endometrium. However, post-menopausal bleeding will be monitored as an AE of special interest and investigators should report any such events to the Sponsor in an expedited manner. This should be done by completing an AE of Special Interest form within 5 working days of awareness of the event and submitting the form to the medical monitor by email. Note, the AESI form should NOT be sent to Emas.

Additionally, any subjects experiencing post-menopausal bleeding after randomisation should undergo a transvaginal ultrasound with subsequent investigation and management (including endometrial biopsy, if indicated) according to the investigator's clinical judgement and usual practice (unexplained post-menopausal bleeding *prior* to randomisation will exclude the subject from the study).

#### **10.5.2 Assessment of Severity**

The severity (intensity) of each adverse event will be classified as:

- **Mild**            Awareness of sign or symptom, but easily tolerated
- **Moderate**      Sign or symptom causes discomfort, but does not interfere with normal activities
- **Severe**           Sign or symptom of sufficient intensity to interfere with normal activities

#### **10.5.3 Assessment of Causality**

A determination will be made of the relationship (if any) between an AE and the study drug. A causal relationship is present if a determination is made that there is a reasonable possibility that the AE may have been caused by the drug or study procedure. AEs will be classified as either related or unrelated.

#### **10.5.4 Adverse Event Reporting**

Adverse events may be volunteered spontaneously by the subject, or discovered as a result of general, non-leading questioning. As the full medical history and physical evaluation does not take place until Screening Visit 2, the adverse event reporting period starts after this visit is

complete. Adverse events occurring from the time of Screening Visit 2 up to the final study visit will be recorded. All AEs should be recorded in the eCRF and in the subjects' source notes.

Any SAE occurring from Screening Visit 2 until 28 days after the last dose of IMP must be reported immediately (within 24 hours of the investigator becoming aware of it) and recorded on the SAE Form. Detailed instructions for the reporting of SAEs can be found in the Study Manual. All subjects with a SAE must be followed up and the outcomes reported. The investigator must supply the Sponsor and the relevant agency/IRB/IEC with any additional requested information (e.g., autopsy reports and terminal medical reports). Any follow-up information on a previously reported SAE will also be reported within 24 hours of awareness.

If the Investigator does not have all information regarding an SAE, he/ she will not wait to receive additional information before reporting the event and completing the appropriate data collection form. The Investigator should always provide a preliminary assessment of causality at the time of the initial report as described in Section 10.5.3.

The primary mechanism for reporting SAEs will be a paper collection form.

Scan & email of the SAE form is the preferred method to transmit this information to the project contact for SAE receipt although fax transmission is also acceptable. In rare circumstances and in the absence of email facilities or fax equipment, notification by telephone is acceptable, with a copy of the SAE data collection form sent by overnight mail. Initial notification via the telephone does not replace the need for the Investigator to complete and sign the SAE data collection form within the designated reporting periods.

If required according to local regulatory authorities and IRB/IEC policy, each Investigator must then notify his or her relevant agency/IRB/IEC of the SAE.

NeRRe is required to expedite to worldwide regulatory authorities reports of SUSARs in line with the relevant legislation. Fatal or life-threatening SUSARs must be reported within 7 calendar days and other SUSARs within 15 calendar days.

In accordance with the European Commission Directive 2001/20/EC, NeRRe will notify the relevant Ethics Committees in concerned Member states of applicable SUSARs as individual notifications or through a periodic line listing. SUSARs will be reported to IRB/EC in non-EU countries according to local regulations and IRB/EC policy.

All investigators will receive a safety letter notifying them of relevant SUSAR reports.

NeRRe (or their designee) will submit to the regulatory authorities all safety updates and periodic reports, as required by applicable regulatory requirements.

## **11. STATISTICAL CONSIDERATIONS**

### **11.1 Estimated Sample Size**

#### **11.1.1 Efficacy**

The total sample size for the trial yields high power for the expected large difference from placebo in hot flush reduction from baseline and adequate power for moderate difference.

Assuming a common standard deviation (SD) of 4.4, N=27 per treatment group has ~95% power ( $\alpha=0.05$  2-sided) via trend test across all doses including placebo if the true underlying dose response is non-decreasing from a reduction of 4 hot flushes on placebo up to 8 on the highest dose of NT-814. N=33 per treatment group is required for 95% power for pairwise comparison of the highest dose to placebo under these same assumptions. Hence, a total of 150 completed subjects (30 x 5) was used for the simulations of adaptive design. [Note, the actual performance / power for the adaptive designs may be higher than the values cited in this report since additional subjects will be added to selected dose groups to better inform on safety.] The actual sample size will be determined by the adaptive dose-finding design algorithm (See Appendix B). In addition, the actual sample size is increased by 10% to allow for subjects who withdraw prematurely and so the initial sample size will be 165 subjects.

The sample size allows for 95% power since each of the four co-primary endpoints are required to demonstrate statistical significance in order to yield a firm conclusion of beneficial treatment effect on hot flushes. Conservatively, assuming independence among the four endpoints, this would yield approximately 81% power overall for achieving statistical significance for each of the four endpoints. Thus, overall power for the trial is estimated to be at least 81%; the actual power depends on the unknown magnitudes of correlations among the co-primary endpoints.

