### **11.9.1 Primary Efficacy Analysis**

The co-primary endpoints are the change from baseline in the mean daily frequencies of moderate and severe hot flushes in the 7 days before the week 4 and Week 12 visits, and the mean severity of moderate and severe hot flushes in the 7 days before the week 4 and Week 12 visits. The baseline assessment will be the last 7 days of the baseline diary completion period. Absolute and

---

changes from baseline in the mean daily frequencies and average hot flush severity will be summarised by treatment group. The change from baseline endpoint will be analysed using a mixed model repeated measures analysis. Pairwise statistical comparisons are planned for each NT-814 dose group (40 mg, 80 mg, 120 mg and 160 mg) versus placebo, presenting the adjusted mean treatment difference with its corresponding 95% confidence interval. In addition, treatment mean comparisons to placebo may be made via estimated means from a 4-parameter Emax model fit and trend test for increasing response with increasing dose based on isotonic regression modelling [details will be in the Statistical Analysis Plan].

The primary objective will be assessed by testing the following hypotheses for each NT-814 group versus placebo separately:

Null hypothesis ( $H_0$ ): There is no difference in the mean change from baseline in hot flush frequency [or severity] at Week 12 [or Week 4] compared to Baseline for the NT-814 treatment group compared to placebo.

$$H_0: \mu (\text{active}) = \mu (\text{placebo})$$

Alternative hypothesis ( $H_1$ ): There is a difference in the mean change from baseline in hot flush frequency [or severity] at Week 12 [or Week 4] compared to Baseline for the NT-814 treatment group compared to placebo.

$$H_1: \mu (\text{active}) \neq \mu (\text{placebo})$$

Absolute and changes from baseline in the in the mean frequency and severity will be summarised by treatment group.

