inhibitors of CYP3A4	boceprevir, cobicistat, danoprevir and ritonavir, elvitegravir and ritonavir, grapefruit juice, indinavir and ritonavir, itraconazole, ketoconazole, lopinavir and ritonavir, paritaprevir and ritonavir and (ombitasvir and/or dasabuvir), posaconazole, ritonavir, saquinavir and ritonavir, telaprevir, tipranavir and ritonavir, troleandomycin, voriconazole  aprepitant, cimetidine, ciprofloxacin, clotrimazole, crizotinib, cyclosporine, dronedarone, fluconazole, fluvoxamine, imatinib, tofisopam, verapamil, troleandomycin, ciprofloxacin
P-glycoprotein inhibitors	azithromycin, conivaptan, cyclosporine, diltiazem, erythromycin, felodipine, ketoconazole, quinidine, ranolazine,  amiodarone, carvedilol, clarithromycin, dronedarone, itraconazole, lapatinib, propafenone, quinidine,
P-glycoprotein substrates with a narrow therapeutic range	Digoxin
Prohibited from Screening Visit 2 until Week 12	
Strong or moderate inducers of CYP3A4	rifampicin, carbamazepine, efavirenz, bosentan, modafinil, St. John's Wort, enzalutamide, mitotane, phenytoin, etravirine

[figure not shown]
**APPENDIX B: PHASE 2B ADAPTIVE DOSE-FINDING DESIGN FOR NT-814  
EFFECT ON REDUCTION OF HOT FLUSHES**[name]  
18 July 2018**INTRODUCTION AND PURPOSE**

A Phase 2b dose-finding placebo-controlled trial of NT-814 treatment with four different doses for 12 weeks aimed at reduction of hot flushes is being planned. Adaptive design options are being considered to modify randomization ratios to the NT-814 doses based on accumulating data. This report summarizes several example adaptive design options along with their performance characteristics for an initial assumed example set of potential TRUE underlying dose-response curves. The primary endpoints for the trial are hot flush frequency and severity; however, the adaptive design simulation software cannot handle multiple endpoints. Hence, the scenarios evaluated focus on reduction of hot flush frequency.

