**METHODS**

First, in order to arrive at some example TRUE underlying dose-response scenarios, prior data on hot flush reduction was examined. NT-814 has shown efficacy in reduction of hot flushes over a 2-week period in a Phase 1/2a trial. Mean reductions in hot flush frequency of up to 9 per day from a baseline frequency ~10-12 were observed (with an observed SD of change from baseline ranged between ~3.4 to ~4.9; SD back-calculated from SE's from the analysis model yielded SD's of change ~3.7). In order to obtain longer term prior data to inform on expected variability, the Duavee label was also examined. It yielded SD's of change ~4.4 after 4 weeks' treatment and ~3.6 after 12 weeks' treatment. Based on these prior data, an SD=4.4 and somewhat conservative magnitudes of treatment effect were used to simulate adaptive design outcomes and performance characteristics. The following TRUE underlying dose-response curves were examined:

label	Assumed TRUE underlying mean hot flush frequency reduction from baseline (SD=4)				
	placebo (dose0)	dose1	dose2	dose3	dose4
DRCID 1	4	4	5	6	7
DRCID 2	4	5	6	7	8
DRCID 3	4	5	6	8	8
DRCID 4	4	6	8	8	8

The total sample size for the trial yields high power for the expected large difference from placebo in hot flush reduction from baseline and adequate power for moderate difference.

Assuming a common standard deviation (SD) of 4.4, N=27 per treatment group has ~95% power ( $\alpha=0.05$  2-sided) via trend test across all doses including placebo if the true underlying dose response is non-decreasing from a reduction of 4 hot flushes on placebo up to 8 on the highest dose of NT-814. N=33 per treatment group is required for 95% power for pairwise comparison of the highest dose to placebo under these same assumptions. Hence, a total of 150 completed subjects (30 x 5) was used for the simulations of adaptive design. [Note, the actual performance / power for the adaptive designs may be higher than the values cited in this report since additional subjects will be added to selected dose groups to better inform on safety.] The actual sample size will be determined by the adaptive dose-finding design algorithm.

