**TABLE 1a - Performance Characteristics (sample sizes, power, early stopping probability)**

TRUE underlying Dose-Response Curve	Design	Number of Cohorts	Average Total Sample Size	Power (%)*	Average Sample Size Assigned Per Dose					Proportion stopped early
					D0 (pbo)	D1	D2	D3	D4	
D0=4, D1=4, D2=5, D3=6, D4=7	Emax	1	150	88	30.0	30.0	30.0	30.0	30.0	0.000
		3	147	90	29.5	25.1	18.4	20.5	53.9	0.028
		6	148	93	29.6	21.6	19.1	22.2	55.3	0.026
	Tstat	1	150	89	30.0	30.0	30.0	30.0	30.0	0.000
		3	144	85	28.8	13.9	23.2	33.3	44.8	0.074
		6	145	89	29.0	15.2	24.4	32.4	44.2	0.066
D0=4, D1=5, D2=6, D3=7, D4=8	Emax	1	150	98	30.0	30.0	30.0	30.0	30.0	0.000
		3	146	99	29.1	30.2	22.3	20.8	43.1	0.056
		6	145	99	29.0	28.1	23.7	21.9	42.4	0.078
	Tstat	1	150	97	30.0	30.0	30.0	30.0	30.0	0.000
		3	146	94	29.3	21.1	30.8	34.0	31.2	0.038
		6	148	96	29.6	24.3	31.7	32.3	30.1	0.026
D0=4, D1=5, D2=6, D3=8, D4=8	Emax	1	150	99	30.0	30.0	30.0	30.0	30.0	0.000
		3	142	98	28.4	31.5	22.9	20.6	38.6	0.112
		6	141	100	28.2	29.7	24.2	21.5	37.2	0.150
	Tstat	1	150	99	30.0	30.0	30.0	30.0	30.0	0.000
		3	148	97	29.6	23.0	35.1	33.4	26.9	0.020
		6	149	98	29.7	25.8	36.4	30.8	25.9	0.016
D0=4, D1=6, D2=8, D3=8, D4=8	Emax	1	150	96	30.0	30.0	30.0	30.0	30.0	0.000
		3	136	95	27.1	39.2	20.1	16.6	32.5	0.186
		6	133	96	26.7	38.1	20.3	17.6	30.6	0.242
	Tstat	1	150	97	30.0	30.0	30.0	30.0	30.0	0.000
		3	146	94	29.2	38.7	34.4	23.6	20.1	0.044
		6	149	97	29.8	42.7	34.4	23.4	18.7	0.010

\*Power to yield statistically significantly increasing trend across doses (i.e., not flat) at alpha=0.025 1-sided

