- (ii) a model based on isotonic regression (T-stat)

The models have been developed using the following prior assumptions:

1) On frequency of hot flushes:

- The mean reduction in the mean daily number of moderate and severe HF's in the placebo group is 4 per day
- Two target levels of test treatment: mean reduction from baseline in the mean daily number of moderate and severe HF's of 6 and 8
- Common standard deviation (SD) of 4.4
- Stopping guidelines for Emax if (a) the probability is > 90% that the mean hot flush reduction is at least 8 at that dose, or (b) the probability is <20% that the mean hot flush reduction is at least 5 (i.e., >80% probability that the mean hot flush reduction is <5).

2) On severity of hot flushes:

- The mean reduction in the severity of moderate and severe HF's in the placebo group is 0.44 per day
- Two target levels of test treatment: mean reduction from baseline in the severity of moderate and severe HF's of 0.66 and 0.88
- Common standard deviation (SD) of 0.55
- Stopping guidelines for Emax if (a) the probability is > 90% that the mean severity hot flush reduction is at least 0.88 at that dose, or (b) the probability is <20% that the mean severity hot flush reduction is at least 0.22 (i.e., >80% probability that the mean hot flush reduction is <0.22).

Emerging data (mean change from baseline in the frequency/severity of moderate and severe HF at Week 4) will be entered in COMPASS software using the Execute module. The following steps will be followed:

- Raw data from eDiaries will be provided to the Cytel blinded team by ERT, the CRF data will be provided by the Pharm Olam Data Management team
- Efficacy endpoints to be presented (see above) will be generated by the Cytel blinded team using the derivation described in this SAP
- Statistical descriptive tables for these endpoints will be produced by the Cytel blinded team using a dummy randomisation list

- Programs will be rerun by the Cytel unblinded team using the real randomisation list provided to the Cytel unblinded statistician
- Endpoint data for each patient along with their treatment arm will be entered into COMPASS.

Prior distributions, defined above and used for the simulation, will also be entered in the software. COMPASS has been developed as a software package for design of adaptive early stage trials within Cytel's suite of software programs for design, analysis, and implementation of clinical trials.

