- lsmeans_: LSM, SE and 95% CI for each treatment at each visit  
- diffs_: Difference in LSM, 95% CI and p value  
- tests3_: overall p values for the fixed effects.
```

The assumption of normality (to ensure that the parametric models are appropriate) will be explored via the visual checks that are based on a normal probability plot of the residuals against their values expected on the normal distribution. If the data are normally distributed then the residuals will roughly form a straight line on the normal plot. If the plotted data deviates markedly from a straight line then it is likely that the data are not normally distributed. In that case, a non-parametric analysis will be used as a sensitivity analysis to complement the parametric MMRM results. A Wilcoxon rank-sum test will be performed at each timepoint (Week 4 and 12) and for each pairwise treatment comparison.

SAS code:

```
PROC NPARIWAY DATA= dataset WILCOXON;  
CLASS treat;  
VAR chg;  
EXACT Wilcoxon;  
WHERE avisit = "Week 4" and treat in ("Placebo","NT-814 40mg");  
RUN;  
* chg represents the mean change from baseline variable;  
* treat represents the treatment group;  
* avisit represents the analysis visits as defined in section 4.2.12.
```

In addition, as a sensitivity analysis, an analysis of covariance (ANCOVA) including terms for treatment group, along with the following baseline covariates: Baseline frequency or severity, Region (section 4.2.3). This analysis will be performed at each timepoint (Week 4 and Week 12).

SAS code:

```
PROC MIXED DATA=dataset;
CLASS treat region;
MODEL chg = treat base region;
LSMEANS treat / pdiff (ref='Placebo') cl;
ODS OUTPUT lsmeans=lsmeans_ tests3 = tests3_ diffs = diffs_
convergenceStatus=convergenceStatus_;
WHERE avisit = "Week 4";
RUN;
* base represents the baseline value of the endpoint;
* chg represents the change from baseline variable;
* treat represents the treatment group;
* region represents the categorical covariate related to stratification factors.
Further options to control the output may be added. See MMRM notes for ODS
OUTPUT.
```

As an ad-hoc analysis, treatment mean comparisons to placebo may be made via estimated means from a 4-parameter Emax model fit and trend test for increasing response with increasing dose based on isotonic regression modelling at Week 4 and Week 12 using the same methodology as described in section 4.3.2.

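### The overall power of at least 81% holds for the optional trend test, not for the primary pairwise tests at 30 completers per arm; severity has no power calculation; SAP 4.1 reverses the variance trigger

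*Protocol*

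**What the plan says.** Protocol 11.1.1 assumes a common SD of 4.4 and a mean reduction of 4 hot flushes on placebo rising to 8 on the highest dose. It gives about 95% power for a trend test with 27 per group. For the pairwise test it states: "N=33 per treatment group is required for 95% power for pairwise comparison of the highest dose to placebo". It then takes 150 completers (30 in each of five arms) as the basis for the simulations and adds 10% for withdrawals, giving 165. Because all four co-primary endpoints must be significant, it credits 95% to each, assumes independence as the conservative case, and concludes: "Thus, overall power for the trial is estimated to be at least 81" per cent. The synopsis and Appendix B (Methods) repeat this. SAP 4.1 repeats the sample-size paragraph but not the 81%.

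On which test is primary, Protocol 11.9.1 says: "The primary objective will be assessed by testing the following hypotheses for each NT-814 group versus placebo separately". The trend test is optional there, and SAP 4.6.1 says: "As an ad-hoc analysis, treatment mean comparisons to placebo may be made via estimated means from a 4-parameter Emax model fit and trend test". The simulated power in Appendix B, Table 1a is trend power, by its footnote: "Power to yield statistically significantly increasing trend across doses (i.e., not flat) at alpha=0.025 1-sided".

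On severity, Appendix B says that "the adaptive design simulation software cannot handle multiple endpoints" and limits its scenarios to frequency. The only severity inputs are those for the interim model in SAP 4.3.2: reductions of 0.44 on placebo and 0.66 or 0.88 on treatment, with "Common standard deviation (SD) of 0.55".

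On re-estimation, SAP 4.1 permits more subjects in the continuing dose groups if either the observed variance or the observed delta turns out below its original estimate. Protocol 8.6.1 permits an increase if the effect and variability estimates prove wrong, without giving a direction.

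**The concern.** The 81% combines a per-endpoint power that belongs to one test with a success rule that is judged by another. The protocol's own paragraph shows that 30 is three per arm short of the pairwise requirement, so calling 81% a minimum is inconsistent with the figures beside it. The same 95% is carried to two severity endpoints with no effect size or SD behind it.

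A reader will take the 81% as the chance that the top dose beats placebo on all four endpoints, because that is how the primary objective is tested.

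The SAP trigger is a separate matter. Whether the sample-size assumptions remain valid is one of the two questions set for the interim reviews in Protocol 11.2. The only direction written down for variance picks out the case that needs no extra subjects and omits the case that does.

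**Working it through.** **Inputs.** Difference 8 − 4 = 4, SD 4.4, two-sided alpha 0.05, 30 completers per arm (Protocol 11.1.1); severity 0.44 against 0.88, SD 0.55 (SAP 4.3.2); alternative SDs from Appendix B, Methods.

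**Method.** Unadjusted two-sample t-test with noncentrality d·√(n/2) and 2n − 2 degrees of freedom, where d = difference/SD. Joint power under independence is the product of the four endpoint powers.

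**The plan's own figures reproduce.**
- 0.95⁴ = 0.8145, the stated 81%.
- Pairwise, d = 4/4.4 = 0.909: the smallest n per arm giving 95% is 33, as stated (n = 33 gives 0.9532).
- Trend, linear contrast on means 4, 5, 6, 7, 8: n = 27 gives 0.960, consistent with about 95%.

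**At the planned 30 per arm, frequency effect on all four endpoints**

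| Test | Power per endpoint | Fourth power |
|---|---|---|
| Trend (linear contrast, 4 to 8) | 0.974 | 0.90 |
| Pairwise, highest dose, t | 0.9335 | 0.759 |
| Pairwise, t with error df pooled over five arms | 0.938 | 0.774 |
| Pairwise, normal approximation | 0.941 | 0.783 |

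All three pairwise versions are below 0.81. If 33 per arm contribute at Week 4 and 30 at Week 12, the product is 0.9532² × 0.9335² = 0.792. If all 33 randomised per arm contribute at both times, it is 0.9532⁴ = 0.826.

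**Severity (assumption: the SAP interim-model values hold at Weeks 4 and 12).** d = 0.44/0.55 = 0.80. Power is 0.861 at 30 per arm and 0.893 at 33; 95% needs 42 per arm. The four-endpoint product at 30 is 0.9335² × 0.861² = 0.647; at 33 it is 0.9532² × 0.893² = 0.724.

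**Correlated endpoints (assumed range).** Correlation between times was varied from 0.3 to 0.9, and between frequency and severity from 0.3 to 0.7, by multivariate normal simulation with 400,000 draws. Joint power at 30 per arm is 78–86% on the frequency effect and 69–79% on the severity values.

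**Adaptive allocation.** These are approximations at the Appendix B average arm sizes for the 4, 5, 6, 7, 8 curve (placebo/top dose), on the frequency effect. T-statistic, three cohorts, 29.3/31.2: 0.935, fourth power 0.765. Emax, three cohorts, 29.1/43.1: 0.962, fourth power 0.857.

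**Variance trigger.** Required n is proportional to SD². Pairwise power at 30 per arm is 0.988 at SD 3.6 and 0.875 at SD 4.9. The latter is the top of the range in Appendix B ("with an observed SD of change from baseline ranged between ~3.4 to ~4.9") and needs 40 per arm for 95%. Lower variance therefore lowers the need for subjects. The delta half of the SAP sentence is correct.

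**The case against.** The strongest reply is that 76% is not a true floor either. Four arguments support it.

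- **SD.** Appendix B reports 4.4 at 4 weeks but about 3.6 at 12 weeks from a product label. Using both at 30 per arm gives 0.9335² × 0.9884² = 0.85. With the model-based 3.7 from the earlier trial, pairwise power is 0.984 and the product 0.94.
- **Primary model.** It is an MMRM adjusted for baseline and region, using all visits. A fall of about 8% in residual variance (SD near 4.22) would restore 95% per endpoint at 30 per arm. Early withdrawals also contribute to it; 32 per arm already gives 0.805.
- **Sample size.** The final size comes from the algorithm, with a cap of 300, and the Emax allocation gives 86%.
- **Independence.** It is declared as a worst case.

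These points stand as reasons why actual power may exceed 76%. They do not rescue the statement as written. Each either departs from the section's own SD of 4.4 and 30 completers or relies on a gain the documents do not quantify, and the T-statistic allocation stays at 76%. They also leave severity open: with SD 3.7 for frequency, the product with the SAP severity values is still 0.9845² × 0.861² = 0.72.

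Two caveats are fair. The severity values are interim-model inputs, and the SAP gives two severity formulas (4.2.11 excludes mild flushes, 4.3.2 includes them), so it is unclear which variable the 0.55 describes. Also, the SAP describes the blinded data review as already held, so the reversed trigger may have had little left to steer. It is permissive wording, but it is still the SAP's stated reason for the 300 cap.

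**Conclusion.** The concern holds. The multiplication is right, but 81% is not a lower bound for the pairwise tests that define the primary objective. On the section's own inputs, power for the highest dose at 30 completers per arm is 93% per endpoint and 76% for all four under independence (78% by normal approximation). This rests on an unadjusted t-test, SD 4.4 throughout, and severity having the same standardised effect as frequency. If the SAP severity values apply, it is about 65%. For the trend test on the 4-to-8 linear curve the 81% is comfortably met (90%), but that test is optional. The 95% for severity has no support in either document. The variance half of the SAP 4.1 trigger is reversed. None of this shows the trial to be unsound; the stated power and one SAP sentence are wrong as written and should be corrected.

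**What to change.** In Protocol 11.1.1, the synopsis and Appendix B, replace the at-least-81% statement with text to this effect: *The figure of about 95% refers to the trend test. For the primary pairwise comparison of the highest dose with placebo, power at 30 completers per arm is about 93% for frequency. Assuming independence, power for all four endpoints is about 76% if severity has the same standardised effect as frequency, or about 65% if the SAP severity assumptions (0.44 against 0.88, SD 0.55) apply. Positive correlation raises both.*

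In SAP 4.1, reword the trigger so that the sample size may be increased *if the observed variance is higher, or the observed delta lower, than originally estimated*.

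The cost is text in three protocol places and one SAP sentence. The primary test, the design and the number of subjects do not change; the stated power becomes less favourable.
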